6.6.2. Dose Limiting Toxicities

DLTs will be summarized for Phase 1b. DLTs will be summarized using descriptive statistics. Frequency counts for each unique DLT will also be presented.

6.6.3. Clinical Laboratory Assessments

Laboratory toxicities will be graded for severity using NCI-CTCAE Version 5.0 (see [Appendix B](#) for more details about laboratory grading). Frequencies and percentages of patients experiencing treatment-emergent grade 3 and 4 toxicities will be summarized.

Descriptive summaries of select quantitative clinical laboratory results (hemoglobin, white blood cells [WBC], absolute neutrophil count [ANC], platelets, blasts count, AST, ALT, alkaline phosphatase, amylase, lipase, total bilirubin, direct bilirubin, serum creatinine, urea nitrogen) and their changes from baseline will be presented by study visit.

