### **2.5.3 Potential for Overlapping Toxicities Resulting from the Combination of LANRA and Gilteritinib**

In the reference safety information for LANRA, liver transaminase elevations are listed as potential adverse drug reactions, based on clinical trial experience to date. Transaminase elevations were infrequent and reversible upon discontinuation of LANRA. A review of the respective toxicity profiles for LANRA and gilteritinib reveals that the most likely overlapping and potentially treatment-limiting toxicity resulting from the combination is liver toxicity (ie, transaminase elevations). Other potential overlapping toxicities include (but are not limited to) rash, constitutional symptoms (fatigue/malaise, myalgia/arthralgia, fever, headache) and gastrointestinal signs/symptoms (nausea, vomiting, diarrhea, abdominal pain, constipation). These can be monitored by close surveillance and conventional safety assessments as described in [Section 11](#); all are potentially manageable with supportive care interventions and study treatment modifications ([Section 8](#)).

Co-administration with gilteritinib is not expected to impact LANRA plasma exposures. An evaluation of PK parameters for LANRA alone and in combination with gilteritinib will be conducted in this study to investigate the potential for meaningful PK interaction between the two.

In consideration of the above, the Sponsor has concluded that the potential benefits of the proposed study outweigh the risks for the following reasons:

- the prognosis for patients with R/R *FLT3*-mutated AML is dismal,
- there are limited effective treatment options available for this subgroup of patients,
- there is significant room for improvement when considering outcomes for patients treated with gilteritinib monotherapy in this clinical setting ([Section 2.2.1](#)),

- there is compelling evidence from non-clinical pharmacologic studies ([Puissant 2014](#)), as well as ex vivo pharmacodynamic studies of leukemic isolates from AML patients to suggest that incremental clinical benefit could be achieved from concurrent inhibition of SYK and FLT3,
- there is preliminary clinical evidence that the SYK inhibitor ENTO (the predecessor to LANRA) may improve CR rates when combined with standard “7 + 3” induction chemotherapy in newly diagnosed patients with *FLT3*-mutated AML ([Walker 2020](#)) and,

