## 5.0 Patient Population

### 5.1 Inclusion Criteria

Participants are eligible to be included in the study only if all the following criteria apply:

1. Adults  $\geq 18$  years of age with AML and at least 1 prior line of therapy.

**Note:** Patients must meet the criteria for a partial response, stable disease or progressive disease as best response after the last prior line of therapy; primary refractory disease after 1st line induction; or recurrence of leukemia after CR, as defined by ELN 2017 response criteria ([Appendix 2](#)).

2. *FLT3*-mutated disease documented in a local reference laboratory at the time of consideration for enrollment in the study.

**Note:** Eligible patients may have either ITD or TKD mutations or both as detected in either peripheral blood or bone marrow.

**Note:** Patients with a history of exposure to midostaurin, other multikinase inhibitor (eg, sorafenib), or 2nd generation *FLT3* inhibitors (including gilteritinib, quizartinib, or crenolanib) for the treatment of AML are eligible but must have discontinued treatment with these agents at least 7 days prior to Cycle 1, Day 1.

3. Have the ability to understand the requirements and procedures of the study and sign a written informed consent form (ICF).
4. Eastern Cooperative Oncology Group (ECOG) performance status (PS) of 0, 1 or 2.
5. Adequate hepatic and renal function defined as:
  - a) serum AST and ALT  $< 2.5$  times the upper limit of normal (ULN); total bilirubin  $< 1.5$  times ULN unless elevated due to Gilbert's Disease or hemolysis
  - b) calculated creatinine clearance  $> 30$  ml/min
6. Prothrombin time (PT), activated partial thromboplastin time (aPTT) and international normalized ratio (INR)  $\leq 1.5$ x ULN unless receiving therapeutic anticoagulation.

**Note:** Transition from a Vitamin K or Factor Xa antagonist to a low-molecular weight heparin preparation is recommended prior to the start of study treatment (see [Appendix 7](#) for guidelines on anticoagulation management).

7. Negative serum  $\beta$ -HCG test in women of child-bearing potential (WOCBP).
8. Left ventricular ejection fraction  $\geq 50\%$  confirmed by echocardiogram (ECHO) or multi-gated acquisition (MUGA) scan.

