- Grade 4 neutropenia or thrombocytopenia lasting > 28 days after treatment onset that is not attributed to active AML and at least possibly related to LANRA.

- Any toxicity resulting in reduction in the dose of LANRA in Cycle 1.

*In general, infection will not constitute a DLT unless it is assessed as having resulted from unexpectedly prolonged myelosuppression in the setting of < 5% blasts in the bone marrow, absence of myelodysplastic changes, and/or absence of AML by flow cytometry in the bone marrow.

Adverse Event

An AE is defined as any unfavorable or unintended sign, symptom, laboratory abnormality or disease (new or exacerbated) temporally associated with the use of a study drug, whether considered causally related to the study drug or not.

All AEs defined as reportable in Section 16.6 of the protocol will be recorded on the ADVERSE EVENTS CRF.

Treatment-emergent Adverse Event (TEAE)

Any adverse event that occurs on or after C1D1 and up to the End-of-Treatment visit following discontinuation of the last study drug is considered treatment-emergent.

Events that occur after the initiation of non-protocol anti-leukemic therapy will be considered as non-treatment emergent even if they occur before the End-of-Treatment visit.

Treatment-emergent Laboratory Toxicity (TELT)

A TELT is identified based on the laboratory data recorded in the eCRF and is defined as a National Cancer Institute - Common Toxicity Criteria for Adverse Events (NCI-CTCAE) v5.0 (NCI 2017) grade 1 or higher abnormality, which occurs on or after C1D1 and up to the End-of-Treatment visit and exhibits at least 1 grade shift from the baseline value.

Events that occur after the initiation of non-protocol anti-leukemic therapy will be considered as non-treatment emergent even if they occur before the End-of-Treatment visit.

Concomitant Medications

Concomitant medications are those medications taken on or after C1D1. This includes medications started prior to C1D1 and continued after C1D1. These medications will be recorded in the PRIOR/CONCOMITANT MEDICATION eCRF.

Prior Medications

Prior medications are those medications taken from the time of informed consent until C1D1. These medications will be recorded in the PRIOR/CONCOMITANT MEDICATION eCRF.

End of Study

After all enrolled patients either relapse or die or 5 years after the last patient enrolls (whichever is earlier) or if the sponsor decides to terminate the trial.

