10. PROPOSED TABLES, LISTINGS, AND FIGURES

Tables	
14.1.1	Subject Disposition and Discontinuation Summary, All Patients Enrolled: Phase 1b
14.1.2.1	Demographics, Safety Population : Phase 1b
14.1.2.2	Baseline Disease Characteristics, Safety Population : Phase 1b
14.1.4.1	Summary of Exposure, Safety Population: Phase 1b
14.1.4.2	Summary of Prior Antileukemic Regimens, Safety Population: Phase 1b
14.2.1	Summary of Best Response by ELN 2017 response criteria, Efficacy Evaluable Population: Phase 1b
14.2.2	Overall Survival, Safety Population: Phase 1b
14.3.1.1	Overview of Treatment Emergent Adverse Events, Safety Population: Phase 1b
14.3.1.2	Treatment-Emergent Adverse Events by System Organ Class, Preferred Term (All Cycles), Safety Population: Phase 1b
14.3.1.3	Treatment-Emergent Non-Serious Adverse Events by System Organ Class, Preferred Term (All Cycles), Safety Population: Phase 1b
14.3.1.4	Grade 3 or 4 Treatment-Emergent Adverse Events by System Organ Class, Preferred Term and Greatest Severity (All Cycles), Safety Population: Phase 1b
14.3.1.5	Treatment-Emergent Serious Adverse Events by System Organ Class, Preferred Term (All Cycles), Safety Population: Phase 1b
14.3.1.6	Treatment Related Adverse Events by System Organ Class, Preferred Term (All Cycles), Safety Population: Phase 1b

14.3.1.7	Treatment Emergent Adverse Events Leading to Dose Reduction by System Organ Class, Preferred Term (All Cycles), Safety Population: Phase 1b
14.3.1.8	Treatment Emergent Adverse Events Leading to Treatment Discontinuation by System Organ Class, Preferred Term (All Cycles), Safety Population: Phase 1b
14.3.1.9	Treatment Emergent Adverse Events Leading to Death by System Organ Class, Preferred Term (All Cycles), Safety Population: Phase 1b
14.3.2	Select Grade 3 or 4 Treatment-Emergent Laboratory Toxicities, All Cycles, Safety Population: Phase 1b
14.3.3	Electrocardiogram by Worst QTcF Results: Phase 1b
Listings	
16.2.1	Subject Disposition, All Patients Enrolled: Phase 1b
16.2.2.1	Informed Consent, All Patients Enrolled: Phase 1b
16.2.2.2	Subject Eligibility, All Patients Enrolled: Phase 1b
16.2.3	Analysis Populations, All Patients Enrolled: Phase 1b
16.2.4.1	Demographics, All Patients Enrolled: Phase 1b
16.2.4.2	General Medical History, All Patients Enrolled: Phase 1b
16.2.4.3	AML Diagnosis, All Patients Enrolled: Phase 1b
16.2.4.4	Additional AML Details, All Patients Enrolled: Phase 1b
16.2.4.5	Prior Systemic Anti-Leukemia Regimens, All Patients Enrolled: Phase 1b

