APPENDIX B: PROGRAMMING MODIFIED NCI-CTCAE GRADING FOR LABORATORY ABNORMALITIES

Category	Analyte Name	CTCAE Term	Grade 1	Grade 2	Grade 3	Grade 4
Chemistry	Albumin	Hypoalbuminemia	<lower limit of normal (LLN) - 3 g/dL	<3 - 2 g/dL	<2 g/dL	-
Chemistry	Amylase	Serum amylase increased	>upper limit of normal (ULN) - 1.5 x ULN	>1.5 - 5.0 x ULN	>5.0 x ULN	-
Chemistry	Alanine Aminotransferase	Alanine aminotransferase increased	>ULN - 3.0 x ULN if baseline was normal; 1.5 - 3.0 x baseline if baseline was abnormal	>3.0 - 5.0 x ULN if baseline was normal; >3.0 - 5.0 x baseline if baseline was abnormal	>5.0 - 20.0 x ULN if baseline was normal; >5.0 - 20.0 x baseline if baseline was abnormal	>20.0 x ULN if baseline was normal; >20.0 x baseline if baseline was abnormal
Chemistry	Alkaline Phosphatase	Alkaline phosphatase increased	>ULN - 2.5 x ULN if baseline was normal; 2.0 - 2.5 x baseline if baseline was abnormal	>2.5 - 5.0 x ULN if baseline was normal; >2.5 - 5.0 x baseline if baseline was abnormal	>5.0 - 20.0 x ULN if baseline was normal; >5.0 - 20.0 x baseline if baseline was abnormal	>20.0 x ULN if baseline was normal; >20.0 x baseline if baseline was abnormal
Chemistry	Aspartate Aminotransferase	Aspartate aminotransferase increased	>ULN - 3.0 x ULN if baseline was normal; 1.5 - 3.0 x baseline if baseline was abnormal	>3.0 - 5.0 x ULN if baseline was normal; >3.0 - 5.0 x baseline if baseline was abnormal	>5.0 - 20.0 x ULN if baseline was normal; >5.0 - 20.0 x baseline if baseline was abnormal	>20.0 x ULN if baseline was normal; >20.0 x baseline if baseline was abnormal

Category	Analyte Name	CTCAE Term	Grade 1	Grade 2	Grade 3	Grade 4
			baseline was abnormal	if baseline was abnormal	if baseline was abnormal	baseline was abnormal
Chemistry	Bilirubin (Total or Direct)	Blood bilirubin increased	>ULN - 1.5 x ULN if baseline was normal; > 1.0 - 1.5 x baseline if baseline was abnormal	>1.5 - 3.0 x ULN if baseline was normal; >1.5 - 3.0 x baseline if baseline was abnormal	>3.0 - 10.0 x ULN if baseline was normal; >3.0 - 10.0 x baseline if baseline was abnormal	>10.0 x ULN
Chemistry	Calcium Corrected for Albumin	Hypocalcemia	<LLN - 8.0 mg/dL	<8.0 - 7.0 mg/dL	<7.0 - 6.0 mg/dL	<6.0 mg/dL
		Hypercalcemia	>ULN - 11.5 mg/dL	>11.5 - 12.5 mg/dL	>12.5 - 13.5 mg/dL	>13.5 mg/dL
Chemistry/ Lipid Profile	Cholesterol	Cholesterol high	>ULN - 300 mg/dL	>300 - 400 mg/dL	>400 - 500 mg/dL;	>500 mg/dL

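### Table 14.3.2 can omit large ALT/AST and bilirubin rises in patients with abnormal baselines, and its cytopenia percentages may include patients who cannot be counted

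*SAP*

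**What the plan says.** SAP 6.6.3 commits to two laboratory summaries. The first is a count of severe toxicities: "Frequencies and percentages of patients experiencing treatment-emergent grade 3 and 4 toxicities will be summarized". The second is a set of descriptive statistics by visit for selected analytes, including ALT, AST, bilirubin, neutrophils and platelets. SAP Section 10 lists one laboratory table, 14.3.2: "Select Grade 3 or 4 Treatment-Emergent Laboratory Toxicities, All Cycles, Safety Population: Phase 1b". It lists no by-visit laboratory table.

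Two rules decide who is counted:

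- **Grading (SAP Appendix B).** Grade 3 ALT or AST is ">5.0 - 20.0 x ULN if baseline was normal; >5.0 - 20.0 x baseline if baseline was abnormal". Bilirubin follows the same pattern up to Grade 3, with cut-offs of 3 and 10; its Grade 4 is fixed at more than 10 x ULN. Neutrophils, platelets and hemoglobin have absolute cut-offs.
- **Treatment emergence (SAP 4.4.4).** An abnormality counts only if it "exhibits at least 1 grade shift from the baseline value".

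Protocol 5.1 admits patients with AST and ALT below 2.5 x ULN and bilirubin below 1.5 x ULN. Bilirubin has no cap when the elevation is due to Gilbert's disease or hemolysis. Neither 5.1 nor 5.2 sets a blood-count limit.

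**The concern.** Safety is the Phase 1b primary objective, and Protocol 2.5.3 says that "the most likely overlapping and potentially treatment-limiting toxicity resulting from the combination is liver toxicity (ie, transaminase elevations". A reader would expect the laboratory table to show how often that happened at each dose. Under Appendix B, a patient who enters with raised liver tests must reach a higher absolute value before being counted, and no output shows ALT/AST and bilirubin rising together in the same patient.

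Blood counts raise a separate issue through a separate rule. Patients with relapsed or refractory AML may enter with severe cytopenia. They cannot satisfy the shift rule, yet they may remain in the denominator, so differences between dose groups can reflect baseline counts.

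The trial stopped after Phase 1b (SAP Section 7), so no later phase will supply a fuller display.

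**Working it through.** The plan states no rate for this table, so there is no figure to reproduce. The check applies the SAP's own rules.

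**Liver tests.** Let b be the baseline in multiples of ULN, with b above 1. Grade 3 then starts above 5b x ULN for ALT/AST and above 3b x ULN for bilirubin. From a normal baseline it starts above 5 and 3 x ULN.

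| Test | Baseline (x ULN) | Grade 3 starts above (x ULN) |
|---|---|---|
| ALT/AST | normal | 5 |
| ALT/AST | 1.2 | 5 x 1.2 = 6 |
| ALT/AST | 1.5 | 5 x 1.5 = 7.5 |
| ALT/AST | 2.0 | 5 x 2.0 = 10 |
| ALT/AST | 2.4 | 5 x 2.4 = 12 |
| Bilirubin | normal | 3 |
| Bilirubin | 1.2 | 3 x 1.2 = 3.6 |
| Bilirubin | 1.4 | 3 x 1.4 = 4.2 |
| Bilirubin | 3.0 (exception only) | 3 x 3.0 = 9 |

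The upper ends of the gap are 5 x 2.5 = 12.5 for ALT/AST and 3 x 1.5 = 4.5 for bilirubin. Neither is quite reached, because both entry limits are strict. Under the Gilbert's/hemolysis exception the bilirubin gap can extend to 10 x ULN, where the fixed Grade 4 limit takes over.

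Example: ALT rises from 2.4 to 11 x ULN and bilirubin from 1.4 to 4 x ULN. The ratios are 11/2.4 = 4.6 and 4/1.4 = 2.9. Both are Grade 2, so the patient is absent from Table 14.3.2. From normal baselines the same values would both be Grade 3.

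The shift rule plays no part here. An abnormal liver test is 1.0 times itself, so it grades as 0 at baseline; the loss comes entirely from the baseline-relative grading.

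**Blood counts.** Neutrophils (per mm³), using the Appendix B cut-offs and the shift rule:

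| Baseline | Worst | Grades | Counted? |
|---|---|---|---|
| 400 | 50 | 4 to 4 | no |
| 700 | 600 | 3 to 3 | no |
| 700 | 300 | 3 to 4 | yes |
| 1200 | 300 | 2 to 4 | yes |

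Let q be the share at Grade 4 at baseline and p the proportion counted among the remaining patients. With the whole Safety Population as denominator, the displayed rate is p(1 − q). The documents give neither p nor q. As an assumed illustration, with p = 50%, q of 20%, 40% or 60% displays as 40%, 30% or 20%.

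**Weight of one patient.** Protocol 4.1 starts cohorts at 3 to 6 patients and caps them at 20. One omitted patient changes a cohort's rate by 1/3 = 33, 1/6 = 17 or 1/20 = 5 percentage points.

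**The case against.** The strongest reply is that other outputs can show such a patient. SAP Section 6 includes minimum and maximum among the descriptive statistics, so a scheduled ALT of 11 x ULN should appear as that visit's maximum in its dose group. Protocol 16.5 makes a clinically significant laboratory abnormality an adverse event, which would then enter the all-grade table 14.3.1.2. Listings 16.2.8.1 and 16.2.8.2 cover selected hematology and chemistry analytes, and with cohorts this small they can be read patient by patient.

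That stands as far as it goes: the values are not lost from the report. But the by-visit summaries have no table in Section 10, and SAP 4.4.4.1 excludes unscheduled visits and keeps only the last value when a test is repeated within a visit. Adverse event recording depends on investigator judgement, and an event graded by the same rule would be Grade 2 and absent from Table 14.3.1.4. None of these outputs gives a laboratory rate by dose or pairs the two tests.

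A second reply is that counting unchanged Grade 4 cytopenia as treatment-emergent would overstate drug toxicity. That is right, and the shift rule should stay. A third is that the denominator is assumed. That is also fair: the table title names the Safety Population, but 6.6.3 does not state the denominator, and Appendix A refers only to the total count in the module.

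A fourth is that the example sits near both entry limits. It does; at a baseline of 1.2 x ULN the ALT threshold moves only from 5 to 6 x ULN.

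**Conclusion.** The point holds as a gap in a descriptive safety display.

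- **Liver.** For baselines within the entry limits, Table 14.3.2 can omit ALT/AST from above 5 to just under 12.5 x ULN and bilirubin from above 3 to just under 4.5 x ULN, or up to 10 x ULN under the exception. This assumes that the last pre-dose value still meets the entry limits. How many patients are affected depends on baseline values that the documents do not give.
- **Cytopenia.** Patients at Grade 4 at baseline, and those who start and stay at Grade 3, are never counted. If they remain in the denominator, the percentage is diluted. The size of this cannot be computed from the documents.

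The documents do not support four stronger readings that a reader might infer:

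- That blood counts are graded against the patient's own baseline. They use absolute cut-offs; the shift rule is what excludes patients.
- That new Grade 4 cytopenias are undercounted. A patient who moves from a lower grade to Grade 4 is counted.
- That liver tests are never assessed in multiples of ULN. They are for every patient with a normal baseline.
- That dose-escalation decisions rest on this table. Protocol 4.1 gives those to the Dose Escalation Committee on the safety, PK and PD data, and prolonged Grade 4 neutropenia or thrombocytopenia has its own DLT criterion in Appendix 1.

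**What to change.** Keep Table 14.3.2. In SAP 6.6.3 and Section 10, add by dose group and overall:

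- **Fixed liver categories.** Patients with peak post-baseline ALT or AST above 3, 5, 10 and 20 x ULN regardless of baseline, and patients with ALT or AST above 3 x ULN together with total bilirubin above 2 x ULN. Include unscheduled values. The lowest cut-offs (3 and 2) lie above the entry limits (2.5 and 1.5), so an eligible baseline value alone cannot fill them, except for bilirubin under the Gilbert's/hemolysis exception.
- **Shift table.** Baseline grade by worst post-baseline grade for neutrophils, platelets, hemoglobin, ALT, AST and bilirubin. State the at-risk denominator separately for each grade row: patients whose baseline grade is below that grade. For the liver tests, use ULN-based grades at both time points, because Appendix B would place every abnormal baseline at grade 0.

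SAP 6.6.6 already reports QTcF both by absolute category and by change from baseline; this gives liver tests the same treatment. The cost is SAP wording and a few extra outputs from data already collected, with no patient burden.

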## 2.5.2 Lanraplenib-associated Toxicities

### 2.5.2.1 Non-clinical data:

Findings associated with administration of LANRA to Sprague-Dawley rats at daily doses up to 100 mg/kg for up to 26 weeks consisted primarily of lymphodepletion in primary and secondary lymphoid organs (thymus, spleen, lymph nodes, bone marrow) accompanied by multifocal bacterial infections, consistent with LANRA's immunomodulatory mechanism of action. Additionally, findings indicative of low-grade hemolysis of uncertain origin in animals treated at the 100 mg/kg dose level were observed.

In addition to lymphodepletion, notable observations associated with administration of LANRA to cynomolgus monkeys at total daily doses  $\geq 20$  mg/kg for 2 weeks or up to 20 mg/kg for 4 weeks included clinical and histopathologic findings consistent with a coagulopathy (ie, ecchymoses, visceral hemorrhage/ulceration and associated inflammatory cell infiltrates). These findings were not replicated in a study of LANRA administered to monkeys for up to 39 weeks at daily doses up to 15 mg/kg and have not been observed in human patients treated with total daily doses up to 50 mg for 7 days or 30 mg for up to

CONFIDENTIAL

Protocol KB-LANRA-1001 v7.0 Global  
(Amendment 6.0 Global)

49.4 weeks (see below). Consult the LANRA Investigator's Brochure (IB; Section 3.3) for additional details on non-clinical safety and PK findings associated with LANRA.

In light of the above-described coagulopathy observed in the 2- and 4-week monkey studies, this study will monitor coagulation parameters including fibrinogen and D-dimer levels, on Days 1 and 15 of Cycle 1, Day 1 of Cycle 2 and Cycle 3 and as clinically indicated thereafter.

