induction or recurrence of leukemia after CR) per ELN criteria (Appendix 2 of the protocol); number of relapses (0, 1, ≥ 2); type of *FLT3* mutation (ITD, TKD or both) and allelic frequency (high, low) at diagnosis (if applicable) and baseline; history of hematopoietic stem cell transplant including post-transplant best response; prior exposure to a *FLT3* inhibitor (e.g. midostaurin and/or selective *FLT3* inhibitor) and presence of other somatic mutations (e.g. *NPM1*, *IDH1*, *IDH2*, *DNMT3A*, *TP53*) at diagnosis and baseline, if known.

^e Obtain triplicate measurements, each separated by approximately 2 minutes with patient in semi-recumbent position at the following timepoints in **Phase 1b**: Screening, C1D1 (pre-dose and paired with PK blood samples at 1, 2, 4, & 6 hours post-LANRA dose), C1D8 (pre- or post-dose), C1D15 (pre-dose and paired with PK blood samples at 1, 2, 4, & 6 hours post LANRA and gilteritinib dosing), C2D1, C3D1 (both pre- or post-dose), and as clinically indicated thereafter. **NOTE:** Pre-dose is considered 0-2 hours before LANRA dosing on C1D1 and LANRA/gilteritinib dosing on C1D15. See Table 4 below for C1D1 paired PK sampling timepoints and Table 5 for C1D15 paired PK sampling time points. In **Phase 2**, obtain triplicate ECG measurements at Screening, C1D8, C1D15, C2D1, and C3D1 (all pre- or post-dose).

^f Record left ventricular ejection fraction and any other clinically relevant findings at Screening. Thereafter, repeat ECHO/MUGA as clinically indicated.

^g Includes hemoglobin, hematocrit, white blood cell (WBC) count, platelet count and WBC differential (neutrophils, bands, lymphocytes, monocytes, eosinophils, basophils, blasts).

^h Includes prothrombin time (PT), activated partial thromboplastin time (aPTT), international normalized ratio (INR), fibrinogen and D-dimer levels. After Screening, monitor coagulation parameters on Days 1 and 15 of Cycle 1, Day 1 of Cycles 2 and 3 and as clinically indicated thereafter.

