16.2.5.1	Drug Accountability, All Patients Enrolled: Phase 1b
16.2.5.2	Exposure Dosing Log, All Patients Enrolled: Phase 1b
16.2.5.3	Cycle Day 1 Dose, All Patients Enrolled: Phase 1b
16.2.5.4	Pharmacokinetic Sampling, All Patients Enrolled: Phase 1b
16.2.5.5	Prior and Concomitant Medications, All Patients Enrolled: Phase 1b
16.2.5.6	Bone Marrow Transplant Post-Study Treatment, All Patients Enrolled: Phase 1b
16.2.6.1	Response Assessment, All Patients Enrolled: Phase 1b
16.2.6.2	Bone Marrow Examination, All Patients Enrolled: Phase 1b
16.2.6.3	Relapse/Progression Assessment, All Patients Enrolled: Phase 1b
16.2.6.4	Relapse Assessment Continued, All Patients Enrolled: Phase 1b
16.2.6.5	Survival Status, All Patients Enrolled: Phase 1b
16.2.7.1	Adverse Events, All Patients Enrolled: Phase 1b
16.2.7.2	Serious Adverse Events, All Patients Enrolled: Phase 1b
16.2.7.3	Deaths, All Patients Enrolled: Phase 1b
16.2.8.1	Laboratory Toxicities – Select Hematology Analytes, All Patients Enrolled: Phase 1b
16.2.8.2	Laboratory Toxicities – Select Serum Chemistry Analytes, All Patients Enrolled: Phase 1b
16.2.8.3	Vital Signs, Height, and Weight, All Patients Enrolled: Phase 1b
16.2.8.4	Physical Examinations – Abnormal Findings, All Patients Enrolled: Phase 1b
16.2.8.5	ECG Central Reading – Triplicate, All Patients Enrolled: Phase 1b
16.2.8.6	Echocardiogram/MUGA, All Patients Enrolled: Phase 1b

16.2.8.7	ECOG Performance Status, All Patients Enrolled: Phase 1b
----------	--

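### The SAP's by-visit laboratory summary omits the coagulation parameters and lymphocytes that LANRA's nonclinical findings point to, and D-dimer and PT reach no named output

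*SAP*

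**What the plan says.** Protocol 2.5.2.1 describes two nonclinical findings for LANRA. In rats, the findings "consisted primarily of lymphodepletion in primary and secondary lymphoid organs", accompanied by bacterial infections. In monkeys, besides lymphodepletion, there were "clinical and histopathologic findings consistent with a coagulopathy" in the 2- and 4-week studies. The section adds a limit: "These findings were not replicated in a study of LANRA administered to monkeys for up to 39 weeks", at doses up to 15 mg/kg, and nothing similar has been seen in humans given up to 50 mg for 7 days or 30 mg for up to 49.4 weeks. Because of the short-term monkey finding, "this study will monitor coagulation parameters including fibrinogen and D-dimer levels, on Days 1 and 15 of Cycle 1" and at later visits.

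The SAP's schedule of assessments (2.2) carries this through. It defines the panel as PT, aPTT, INR, fibrinogen and D-dimer and, after Screening, tells sites to "monitor coagulation parameters on Days 1 and 15 of Cycle 1, Day 1 of Cycles 2 and 3 and as clinically indicated thereafter". Lymphocytes are part of the white-cell differential.

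On reporting, SAP 6.6.3 plans two things. One is a count of patients with treatment-emergent Grade 3 and 4 laboratory toxicities. The other is a by-visit summary of values and changes from baseline for "select quantitative clinical laboratory results (hemoglobin, white blood cells [WBC], absolute neutrophil count [ANC], platelets, blasts count, AST, ALT, alkaline phosphatase", then amylase, lipase, total and direct bilirubin, creatinine and urea nitrogen. In Section 10, the toxicity table (14.3.2) is restricted to a selection that is not specified. The laboratory listings are one for selected hematology analytes and one for "Select Serum Chemistry Analytes, All Patients Enrolled: Phase 1b".

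**The concern.** The protocol gives a reason for drawing the coagulation panel, and names two of its analytes. A reader of the study report would expect to see how those analytes moved, by dose. The SAP's list of analytes is explicit, so a programmer who follows it exactly will not produce that summary.

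Safety is the primary objective of Phase 1b, and SAP 7 states that Phase 2 was not enrolled, so these data are all the trial will provide. The dose range also goes past the human experience that Protocol 2.5.2.1 cites. The 60 and 90 mg cohorts exceed the earlier 50 mg maximum. The 40 mg cohort exceeds the earlier experience only in duration, since 40 mg lies above the long-term 30 mg dose. A moderate dose-related fall in fibrinogen or lymphocytes, or a rise in D-dimer, would be measured but might be visible in no summary.

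**Working it through.** No sample-size or power figure is involved. The check sets what is collected against each route by which the SAP could report it.

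**By-visit list (SAP 6.6.3).** Eight analytes stand in the part quoted (hemoglobin, WBC, ANC, platelets, blasts, AST, ALT, alkaline phosphatase) and six follow, so 8 + 6 = 14. Coagulation parameters among them: 0 of 5. Lymphocytes: absent, although the SAP glossary defines an abbreviation for the absolute lymphocyte count. Total WBC is no substitute in this disease, because the differential it covers includes blasts.

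**All routes together.**

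| Analyte | By-visit change | Appendix B grade | Grade 3-4 summary | Named listing in Section 10 |
|---|---|---|---|---|
| Fibrinogen | no | 1-4 | possible, if selected | none |
| aPTT | no | 1-3 | possible, if selected | none |
| INR | no | 1-3 | possible, if selected | none |
| PT | no | no row | no | none |
| D-dimer | no | no row | no | none |
| Lymphocytes | no | decrease 1-4; increase 2-3 | possible, if selected | possibly in selected hematology |

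So 3 of 5 coagulation parameters can reach the toxicity summary, and 2 of 5 (PT and D-dimer) cannot. D-dimer is one of the two that the protocol names.

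**How coarse the toxicity summary is.** Under Appendix B, Grade 3 begins at INR above 2.5, aPTT above 2.5 x ULN, fibrinogen below 0.5 x LLN (or a fall of at least 50% if already abnormal), and lymphocytes below 500/mm³. An INR that moves from 1.0 to 2.4 is Grade 2 and enters no planned laboratory table. So is a fibrinogen that falls from normal to 0.5 x LLN.

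**Listings.** SAP 4.4.4.1 says that all data will be listed. SAP 6 says that only some will. Section 10, headed as proposed outputs, names no coagulation listing. The text does not settle which statement governs.

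**Volume, as a ceiling only.** Scheduled draws are at Screening, C1D1, C1D15, C2D1 and C3D1. With 5 parameters, 5 time points and at most 69 Phase 1b patients (SAP 4.2), 5 x 5 x 69 = 1,725 results. The true number will be lower: 69 is a maximum, the C1D1 draw can be waived if Screening fell within 48 hours, and C3D1 requires the patient still to be on treatment.

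**A related detail.** Section 10 has no numbered table for the by-visit laboratory summary at all, even for the 14 analytes.

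**The case against.** The strongest reply is that other routes exist. The Grade 3-4 sentence in SAP 6.6.3 carries no analyte restriction, and writing Appendix B rules for fibrinogen, aPTT, INR and lymphocytes suggests that they are meant to be used. Protocol 16.5 makes clinically significant abnormal results adverse events. It names coagulation studies explicitly, and its threshold is fairly low. Bleeding and infection would be reported as adverse events too. This stands, and it means that severe or clinically evident effects would probably be seen. It does not supply a by-dose view of moderate change, and Table 14.3.2 leaves inclusion open.

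Second, the nonclinical signal is qualified. The coagulopathy was not replicated at up to 39 weeks and has not been seen in humans; lymphodepletion is described as consistent with the mechanism; and Protocol 2.5.3 puts liver toxicity first among overlapping risks, with AST, ALT and bilirubin all in the list. This is fair and limits the weight of the point. The 39-week study stopped at 15 mg/kg, however, while the shorter ones reached 20 mg/kg, so it does not exclude a dose-related effect.

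Third, an isolated INR value may have another cause, because inclusion criterion 6 exempts patients on therapeutic anticoagulation. That is true, and it is a reason to show the distribution by dose level rather than rely on single values.

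Three stronger readings are tempting, and the documents do not support them:

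- A reader might infer that two named LANRA risks will go largely unreported. The toxicity summary and the adverse event tables contradict that.
- A reader might infer that coagulation data will not be listed. The SAP is inconsistent on this, and its inconsistency does not establish an omission.
- A reader might infer a breach of the protocol. Protocol 15.2.7 promises changes from baseline only for selected assessments and names none, and 2.5.2.1 commits to monitoring, not to a table.

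**Conclusion.** The point holds as a reporting gap. None of the five coagulation parameters, and no lymphocyte count, is in the 14-analyte by-visit summary. Two of the five, D-dimer and PT, have no grade, no summary and no named listing. D-dimer is the clearest case, because the protocol names it as a monitoring target; PT matters less, since INR is graded. For fibrinogen, aPTT, INR and lymphocytes, what is missing is change by visit and dose level below Grade 3, together with certainty that they are in Table 14.3.2.

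This rests on reading the list in 6.6.3 as complete and Section 10 as the intended set of outputs. If the statement in 4.4.4.1 governs, individual coagulation values would be listed, but still not summarised. No effect on a trial conclusion can be quantified from the documents. It is a cheap improvement, not a flaw that undermines the analysis.

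**What to change.** - In SAP 6.6.3, add fibrinogen, D-dimer, PT, aPTT, INR and absolute lymphocyte count to the by-visit summary of values and changes from baseline, by dose level. Give that summary a table number in Section 10.
- Name aPTT, INR, fibrinogen and lymphocytes among the toxicities in Table 14.3.2.
- Add a coagulation listing to Section 10, covering all five parameters.
- Reconcile SAP 4.4.4.1 with SAP 6 on whether all or only some data are listed.

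Shift tables over all grades would be a useful option for the graded analytes but are not needed to close the gap; PT and D-dimer could not be included under Appendix B as written.

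The cost is SAP wording, six more rows in a summary that the text already promises, and one more listing. No new data are needed.
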